### 1.3.2. Part B: Repeat Dose Administration in Healthy Participants

FU= Follow up

EW = Early withdrawal

| Procedure (Part B)                      | Screening
(up to 28
days before
Day 1) | Day
-1 | Day
1 | Day
2-6 | Day
7 | Day
8-13 | Day
14 | Day
15 | Day
18-
20 | FU | EW | Notes  |
|---|---|-----------|----------|------------|----------|-------------|-----------|-----------|------------------|----|----|--|
| Outpatient Visit                        | X   |           |          |            |          |             |           |           | X                | X  | X  |  |
| Admission to Clinical Unit              |   | X         |          |            |          |             |           |           |                  |    |    |  |
| Inpatient stay at Clinical Unit         |   | <----->   |          |            |          |             |           |           |                  |    |    |  |
| Discharge from unit                     |   |           |          |            |          |             |           | X         |                  |    |    |  |
| Informed Consent                        | X   |           |          |            |          |             |           |           |                  |    |    |  |
| Inclusion and exclusion criteria        | X   | X         |          |            |          |             |           |           |                  |    |    |  |
| Demography                              | X   |           |          |            |          |             |           |           |                  |    |    |  |
| Medical/medication/drug/alcohol history | X   | X         |          |            |          |             |           |           |                  |    |    |  |
| Physical Exam                           | X   | X         |          |            | X        |             |           | X         |                  | X  | X  | 
 
• Full Physical at screening with height and weight.
 
• Brief physical on all other occasions.
 
 |

| Procedure (Part B)                                  | Screening
(up to 28
days before
Day 1) | Day
-1 | Day
1 | Day
2-6 | Day
7 | Day
8-13 | Day
14 | Day
15 | Day
18-
20 | FU | EW | Notes  |
|---|---|-----------|----------|------------|----------|-------------|-----------|-----------|------------------|----|----|--|
| Vital Signs (BP, HR, Temperature, respiratory rate) | X   | X         | X        | X          | X        | X           | X         | X         |                  | X  | X  | 
 
Days 1, 7 and 14; within 1 hour before the start of AM dose (pre-dose) and at 1, 2, 4, 12, and 24 hours after AM dose.
 
Days, 3, 4, 5, 6, 9, 10, 11, 12, and 13; within 1 hour before the start of AM dose (pre-dose).
 
BP measurements in triplicate and average recorded in CRF.
 
   |
| 12-Lead ECG   | X   |           | X        | X          |          | X           |           | X         |                  | X  | X  | 
 
Triplicate 12-lead safety ECGs will be obtained no more than 2 minutes apart at screening and within 1 hour before the start of AM dose (pre-dose) on Days 1, 6, 10 and 14
 
Single measurements will be obtained at follow up/ EW and Days 1 & 14 at, 30min, 1hr, 2hr, 4hr, 12hr, and 24hr post AM dose.
 
   |
| Telemetry   |   |           | X        |            |          |             | X         |           |                  |    |    | 
 
Telemetry from -1h (i.e., 1h pre-dose) to 24h on Day 1 and Day 14
 
  |
| 24h Holter ECG                                      |   |           |          | X          |          |             |           |           |                  |    |    | 
 
From 1h pre-dose to 24h.
 
ECG extractions at 3 time points prior to dosing and all post-dose PK time points up to and including the 24 h timepoint.
 
Participants will be resting in a semi-recumbent position for at least 15 min at each PK time point for ECG extractions.
 
When ECG extractions and/or safety ECGs coincide with vital signs assessment and blood draws, procedures should occur in the following order; ECGs vital signs blood draws.
 
 |

| Procedure (Part B)                                    | Screening
(up to 28
days before
Day 1) | Day
-1 | Day
1 | Day
2-6 | Day
7 | Day
8-13 | Day
14 | Day
15 | Day
18-
20 | FU | EW | Notes   |
|---|---|-----------|----------|------------|----------|-------------|-----------|-----------|------------------|----|----|---|
| Clinical Labs (Chemistry, Hematology, and Urinalysis) | X   | X         |          | X*         | X        | X*          |           | X         | X*               | X  | X  | 
 
*Day 3, Day 11 and 1 visit only on any day between Day 18-20
 
Sample collected following a fast of at least 8 hours.
 
  |
| Serum Pregnancy test                                  | X   | X         |          |            |          |             |           | X         |                  | X  | X  | 
 
In WOCBP only
 
Day 14 test to be taken after PM dose.
 
   |
| Estradiol/FSH   | X   |           |          |            |          |             |           |           |                  |    |    | 
 
If indicated
 
  |
| Covid 19 test   |   |           |          |            | X        |             |           |           |                  |    |    | 
 
Covid-19 testing to be performed according to local site procedures.
 
Minimum testing; prior to admission to the unit and prior to discharge from the unit.
 
 |
| Urine Cotinine, Drug & Alcohol Test                   | X   | X         |          |            |          |             |           |           |                  |    |    |   |
| HIV, Hep B, Hep C                                     | X   |           |          |            |          |             |           |           |                  |    |    |   |

| Procedure (Part B) | Screening
(up to 28
days before
Day 1) | Day
-1 | Day
1 | Day
2-6 | Day
7 | Day
8-13 | Day
14 | Day
15 | Day
18-
20 | FU | EW | Notes   |
|--------------------|---|-----------|----------|------------|----------|-------------|-----------|-----------|------------------|----|----|---|
| Meals              |   | X         | X        | X          | X        | X           | X         | X         |                  |    |    | 
Breakfast
 
 
Participants will fast 8hr and a standard breakfast will be given approximately 30 min pre dose (except on Day 3 and Day 5 (see below)). On day 7 breakfast will be eaten within 20 minutes.
 
Day 3 - Participants will fast 8hr and will be dosed fasted, a low-fat breakfast will be served approximately 2hr after dosing.
 
Day 5 - Participants will fast 8hr a high fat breakfast meal will be given approximately 30 min. pre dose & eaten within 20 minutes.
 
 
Lunch
 
 
Day 12 in the cohort undergoing bile sampling - A high fat small lunch meal will be served at approximately 5 hours post dose.
 
On all other day's lunch and snacks will be served according to the sites schedule.
 
 
Dinner
 
 
On D1 dinner will be served approximately 1 h before PM dose. On all other days the dinner meal will be given approximately 40 mins prior to the PM dose.
 
 
Fluids
 
 
Water permitted on an ad lib basis
 
Other decaffeinated drinks allowed by the protocol will be permitted except during fasting periods and while the EnteroTracker is in place.
 
 |

| Procedure (Part B)               | Screening
(up to 28
days before
Day 1) | Day
-1 | Day
1 | Day
2-6 | Day
7 | Day
8-13 | Day
14 | Day
15 | Day
18-
20 | FU | EW | Notes  |
|----------------------------------|---|-----------|----------|------------|----------|-------------|-----------|-----------|------------------|----|----|--|
| Bile sampling                    |   |           |          |            |          | X           |           |           |                  |    |    | 
 
Day 12
 
For the highest dose cohort only: EnteroTracker swallowed 2 h post-AM dose.
 
5 h post dose a food stimulus will be administered.
 
After 6 hr post dose the string will be removed.
 
   |
| Dosing                           |   |           | X        | X          | X        | X           | X         |           |                  |    |    | 
 
BID dosing PM dose to be administered 10 hours after AM dose.
 
  |
| Blood sample for PK              |   |           | X        | X          | X        |             |           | X         |                  |    |    | 
 
Days 1 and 14 - blood samples will be obtained predose within 30 minutes prior to AM dose and then post AM dose at the following timepoints: 20mins, 40mins, 1h, 1.5h, 2h, 3h, 4h, 6h, 10h (10 mins prior to PM dose), 10h 20 min, 10h 40min, 12h, 12.5h, 13h, 14h, 16h, and 24 h (within 10 minutes or less prior to next AM dose).
 
Days 3, 5, and 7 - blood samples will be obtained predose within 30 minutes prior to AM dose and then postdose at the following timepoints: 20mins, 40mins, 1h, 1.5h, 2h, 3h, 4h, 6h, 10 (approximately 10 mins prior to PM dose).
 
 |
| Blood sample for Metabolites     |   |           |          | X          |          |             |           | X         |                  |    |    | 
 
Blood samples for metabolite profiling will be collected at all PK timepoints up to 24h.
 
   |
| Urine collection for Metabolites |   |           | X        |            |          |             | X         |           |                  |    |    | 
 
Urine samples will be collected pre-dose and over 0-24 hours.
 
  |

| Procedure (Part B)             | Screening
(up to 28
days before
Day 1) | Day
-1 | Day
1 | Day
2-6 | Day
7 | Day
8-13 | Day
14 | Day
15 | Day
18-
20 | FU | EW | Notes   |
|--------------------------------|---|-----------|----------|------------|----------|-------------|-----------|-----------|------------------|----|----|---|
| 4β-hydroxycholesterol sampling |   |           | X        |            |          |             |           | X         |                  |    |    | 
 
• Sample to be taken pre-dose on Day 1 in a fasted state.
 
• Sample to be taken at 24hr post AM dose on Day 14. Sample should be in a fasted state.
 
 |
| AE Assessment                  |   |           | <----->  |            |          |             |           |           |                  | X  |    |   |
| SAE Assessment                 |   | <----->   |          |            |          |             |           |           |                  | X  |    |   |
| Concomitant Medication Review  |   | <----->   |          |            |          |             |           |           |                  | X  |    |   |

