## 2.3. Benefit/Risk Assessment

### 2.3.1. Risk Assessment

| Potential Risk of Clinical Significance | Summary of Data/Rationale for Risk  | Mitigation Strategy  |
|---|---|--|
| Study Intervention(s)            |   |  |
| Idiosyncratic hepatotoxicity            | 
Covalent binding in hepatic microsomes and the formation of glutathione adducts were observed in vitro. 4-week GLP rat and dog studies have not revealed any adverse effects on the liver.
 
The in vitro findings suggest a potential for immune-mediated idiosyncratic hepatotoxicity. However, idiosyncratic hepatotoxicity is a rare event, and the risk to participants in early clinical trials of short treatment duration is low.
 | 
Participants with hepatic disorders or liver laboratory abnormalities will be excluded from the study.
 
Standard monitoring of LFTs will be implemented per Section 1.3, Section 10.2, and Section 10.5.
 
Liver chemistry stopping criteria will be used as per Section 7.1.1 and Section 10.5.
 
Paracetamol usage will be restricted (max 2g/d, 500 mg at a time).
 |
| Effect on vital signs (HR and BP)       | Increased blood pressure and/or heart rate have been observed in rats and dogs. These changes in vital signs were mild and transient, and the risk of significant changes in heart rate   | 
Monitoring of vital signs will be conducted as per Section 1.3.
 
Stopping criteria related to changes in vital signs will be implemented as per Section 7.1.3.
  |

| Potential Risk of Clinical Significance   | Summary of Data/Rationale for Risk   | Mitigation Strategy  |
|---|--|--|
|   | or blood pressure in humans is considered low.   |  |
| Effect on human embryo/fetus  | 
Preliminary animal embryofetal studies suggest minimal risk for the developing human embryo or fetus. Females of reproductive potential (FRP) can receive GSK3915393 in a clinical study if they use proper contraception as required by the study protocol to avoid pregnancy while taking part in the study.
  | 
Pregnant women will not be eligible to participate.
 
Participating FRPs will agree to comply with the study contraception requirements. Participants will be withdrawn from the study if the participants become pregnant during the study
 
Pregnancy tests will be done at screening, before dosing, and after completion of dosing.
 |

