## 3. OBJECTIVES AND ENDPOINTS

| Objectives   | Endpoints   |
|--|---|
| Primary   |   |
| 
Part A Dose Escalation Single Dose
 
 
• To evaluate the safety and tolerability of single escalating oral doses of GSK3915393 administered in the fed state in healthy adult participants
 
 
Part B Dose Escalation Repeat Dose
 
 
• To evaluate the safety and tolerability of repeat escalating oral doses of GSK3915393 twice daily (BID) administered in the fed and fasted state in healthy adult participants
 
 | 
Part A and B
 
 
• Occurrence of serious adverse events (SAEs), adverse events (AEs) and treatment related AEs
 
• Occurrence of clinically significant changes in physical examination, vital signs, laboratory parameters, and 12-lead electrocardiogram (ECG) findings.
 
 |

| Objectives  | Endpoints   |
|---|---|
| Part C CYP3A4 Victim Interaction 
 
• To characterize the PK profile of IV GSK3915393 administered alone and when co-administered with itraconazole in healthy adult participants
 
• To characterize the PK profile of oral GSK3915393 administered alone and when co-administered with grapefruit juice or with itraconazole in healthy adult participants
 
                 | Part C 
 
• Cmax, Tmax, AUC(0-t), (AUC(0-∞)) and (t1/2) as appropriate
 
   |
| Secondary  |   |

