## 4.2. Scientific Rationale for Study Design

The study design is based on well-established and published methods to evaluate the first single and repeat dose administration of experimental drugs including the use of sentinel dosing. This study includes a placebo arm to allow for a valid evaluation of adverse events attributable to treatment versus those independent of treatment.

A cross-over design is preferred for part A where each participant receives placebo as it allows assessment of safety in the same individual thus reducing the influence of inter-individual variability.

An IV microdose arm has been included Part A in order to determine the absolute bioavailability of GSK3915393 at clinically relevant doses.

Initial evaluation of safety, tolerability, and PK of GSK3915393 in the single ascending dose and multiple ascending dose phases of the study will be conducted in healthy participants. It is prudent to examine safety in participants for 14 days in part B to inform future clinical studies.

Because the solubility of GSK3915393 is pH dependent (high solubility at low pH and low solubility at higher pH), it is likely that the absorption of GSK3915393 will be higher when administered with food particularly at higher doses due to longer retention time in the stomach which will allow greater dissolution time for GSK3915393. For the single ascending dose phase GSK3915393 will therefore be administered in the fed state, following a standard breakfast. In part B, the impact of prandial state (high-fat meal, standard meal and fasted) on the PK of GSK3915393 will be determined at each dose level to determine the appropriate dosing conditions for future clinical studies

Recent *in-vitro* studies have shown that GSK3915393 is a substrate for both intestinal (gut) and hepatic CYP3A4. The impact of moderate CYP3A4 inhibitors and CYP3A4 inducers that may be included in future clinical trials can be modelled based on data from

a strong inhibitor such as itraconazole therefore coadministration of GSK3915393 with itraconazole will be evaluated in part C. Initially an IV microdose (100 µg) of GSK3915393 will be used in Periods 1 and 2 to evaluate the impact of itraconazole inhibition of hepatic CYP3A4 on the systemic exposure to GSK3915393. This data will be used to select the oral dose of GSK3915393 to be used in Periods 3 to 5 (Section 4.3.9). The oral dose to be used in Part C will not exceed 20 mg.

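### Part B's primary objective covers fed and fasted dosing, but no post-dose vital signs, 12-lead safety ECG or telemetry are scheduled on the fasted day (Day 3) or the high-fat day (Day 5)

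*Protocol*

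**What the plan says.** Protocol Section 3 gives the Part B primary objective as "To evaluate the safety and tolerability of repeat escalating oral doses of GSK3915393 twice daily (BID) administered in the fed and fasted state". Its endpoints include "Occurrence of clinically significant changes in physical examination, vital signs, laboratory parameters, and 12-lead electrocardiogram (ECG) findings". SAP Table 2 carries the same objective.

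The meal plan is in Protocol 1.3.2, 4.1.2 and 5.3.1.2. The morning dose follows a standard breakfast except on two days. For the fasted day: "Day 3 - Participants will fast 8hr and will be dosed fasted, a low-fat breakfast will be served approximately 2hr after dosing". On Day 5 a high-fat breakfast precedes the dose. SAP 1.2 repeats the assignment: Day 3 fasted, Day 5 high fat, Day 7 standard.

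The notes to the Part B schedule (Protocol 1.3.2) set the safety readings:
- **Vital signs.** Days 1, 7 and 14 have a pre-dose reading and readings at 1, 2, 4, 12 and 24 h after the morning dose. The remaining listed days are pre-dose only: "Days, 3, 4, 5, 6, 9, 10, 11, 12, and 13; within 1 hour before the start of AM dose (pre-dose".
- **12-lead ECG.** Triplicates are taken at screening and "within 1 hour before the start of AM dose (pre-dose) on Days 1, 6, 10 and 14". Post-dose singles are at 30 min, 1, 2, 4, 12 and 24 h on Days 1 and 14.
- **Telemetry.** Days 1 and 14.
- **Holter.** One 24 h recording is marked under Days 2-6. The note names no day.
- **PK.** Days 3, 5 and 7 have samples from 20 min to 10 h.

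Protocol 2.3.1 lists an effect on vital signs as a potential risk: "Increased blood pressure and/or heart rate have been observed in rats and dogs". The stated mitigation is vital-sign monitoring under Section 1.3, which includes this schedule. On food, Protocol 4.2 says "it is likely that the absorption of GSK3915393 will be higher when administered with food particularly at higher doses".

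**The concern.** The objective names two prandial states, but the scheduled post-dose readings sit in only one of them, the standard breakfast. On the two days when the morning meal is changed on purpose, exposure is profiled and blood pressure, pulse and ECG are not read after the dose. An asymptomatic rise in blood pressure after the fasted or high-fat dose would not appear in any planned safety table.

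This matters in three ways. The vital-sign and ECG endpoints cannot describe the period around peak concentration in those states. The dose-escalation review (Protocol 6.5) uses vital signs and ECG alongside PK, and would have PK but no matching readings for those meals. Protocol 4.2 also wants Part B to inform dosing conditions for later studies, where the meal instruction should rest on tolerability as well as exposure.

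**Working it through.** The plan gives no figure on this point. Its only numbers for Part B safety are the exact 95% upper limits in Protocol 9.2. These reproduce by Clopper-Pearson as 33.63% for 0/9 and 48.25% for 1/9, against 33.6% and 48.2% printed. Nothing below depends on them.

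**Step 1: count scheduled readings after the morning dose** (notes to Protocol 1.3.2). The evening dose is at 10 h, so readings at 12 and 24 h follow a second dose. Counts are given in total and before the evening dose.

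| Day | Morning meal | PK samples to 10 h | Vital-sign times: total / before evening dose | 12-lead ECGs: total / before evening dose | Telemetry |
|---|---|---|---|---|---|
| 1 | standard | 9 | 5 / 3 | 6 / 4 | yes |
| 3 | fasted | 9 | 0 / 0 | 0 / 0 | no |
| 5 | high fat | 9 | 0 / 0 | 0 / 0 | no |
| 7 | standard | 9 | 5 / 3 | 0 / 0 | no |
| 14 | standard | 9 | 5 / 3 | 6 / 4 | yes |

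The three vital-sign times are 1, 2 and 4 h; the four ECG times are 30 min, 1, 2 and 4 h.

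**Step 2: can neighbouring readings stand in?** The predicted half-life is below 2 h (Protocol 4.3.1). Take 2 h as the upper bound, with fraction remaining = 0.5^(t/2).
- The same-day pre-dose reading precedes the test dose and cannot reflect it.
- The next pre-dose reading (Day 4 or Day 6) is 23-24 h after the test dose: 0.5^11.5 = 0.03% and 0.5^12 = 0.02% remain. If the peak came as late as 4 h (an assumption), 19-20 h of decline leaves 0.5^9.5 = 0.14% to 0.5^10 = 0.10%.
- By then an evening dose has been given 13-14 h earlier, of which 0.5^6.5 = 1.1% to 0.5^7 = 0.8% remains. What little drug is present comes mainly from that dose.

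**Step 3: do other parts of the study fill the gap?**
- Part A: oral doses are planned up to 320 mg with post-dose vital signs and ECGs, all after a standard breakfast (Protocol 1.3.1, 5.3.1.1).
- Part C: oral doses are fasted, with vital signs and ECGs at 30 min, 1, 2, 4, 12 and 24 h, but as single doses of at most 20 mg (Protocol 1.3.3, 4.1.2). Part B may reach 160 mg BID (Protocol 4.3.7).
- High-fat meal: no part schedules a post-dose vital sign or 12-lead safety ECG.

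**The case against.** The strongest reply is that the objective may simply describe how Part B doses are given. Safety is summarised by dose regimen over time (Protocol 9.4.1, SAP 4.2), no comparison by meal is planned, and food effect is a separate secondary PK objective. The fasted dose is 1 of 28 (14 days, two doses a day). That is a fair reading, and it is why narrowing the objective is an acceptable alternative. It does not explain why the objective names the fasted state when two of its endpoint components have no post-dose reading there.

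Several stronger conclusions are tempting, and the documents do not support them:
- **That no ECG of any kind is recorded.** The Holter mark falls under Days 2-6, and the PK profile days in that span are 3 and 5. The day is unclear, because the note asks for extractions up to 24 h while PK on Days 3 and 5 stops at 10 h. Wherever it falls, Holter gives no blood pressure, is extracted only if a cardiodynamic evaluation is undertaken (Protocol 8.2.3.1) and is not reported in the primary CSR (Protocol 4.2).
- **That the blood pressure and heart rate risk goes unobserved.** Participants are monitored inpatients, adverse events are collected throughout, standard-meal readings exist, and the vital-sign stopping rule in Protocol 7.1.3 is not limited to scheduled readings. Protocol 2.3.1 calls the animal changes mild and transient and the human risk low.
- **That later meal instructions would rest on adverse events alone.** Part C supplies fasted post-dose readings, though at low dose.
- **That Day 5 must be the highest-exposure day.** The protocol expects more absorption with food than without. It does not rank high-fat above standard meals, and its reasoning makes fasting the lower-exposure state.
- **That the contrast is 0 against 5 vital-sign times and 0 against 6 ECGs.** The 12 and 24 h readings follow the evening dose, so the like-for-like contrast is 0 against 3 and 0 against 4.

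**Conclusion.** The point holds as a cheap improvement. On the only fasted and only high-fat morning doses in the protocol text, there are no scheduled post-dose vital signs, 12-lead safety ECGs or telemetry, while nine PK samples are drawn on each day. Nothing else in the study supplies post-dose blood pressure in the fasted state at Part B doses above Part C's 20 mg ceiling, or after a high-fat meal at any dose. No sample-size or precision figure is affected.

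Three assumptions matter:
- The residual-drug calculation uses the predicted half-life and supposes that any effect on blood pressure or pulse follows plasma concentration.
- The count takes the schedule's notes as the authority for days and times, because column positions in the table are not reliable enough.
- A file note cited in the SAP (version history and references) changed feeding in Part B Cohort 2, and its content is not available. It is therefore not certain that Days 3 and 5 are the only fasted and high-fat days in every cohort. If the note made Day 14, for example, a fasted day, that day's readings would cover part of the gap.

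**What to change.** In Protocol 1.3.2, for cohorts not yet dosed, add vital signs at 1, 2 and 4 h after the morning dose on the fasted and high-fat days, just before the PK draws already scheduled at those times. On the fasted day, take the 2 h reading before the breakfast due at about that time. A single 12-lead ECG at the same times is optional and should precede the vital signs. Apply this to whichever days are fasted and high-fat once the Cohort 2 file note is taken into account.

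Show these readings by meal condition in the dose-escalation outputs and the CSR safety displays, with a line in SAP 4.2 or the Output and Programming Specification. State the Holter day in the schedule.

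If the readings are not added, narrow the Part B objective in Protocol Section 3 and SAP 1.1 to match what is measured. For cohorts already dosed, state the limitation in the CSR.

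The cost is three vital-sign sets on each of two days (and three single ECGs per day if chosen), in participants who are already in-house and being bled at those times. No visit or equipment is added. Protocol 1.3 lets time points be added with documentation and without a protocol amendment; narrowing the objective would change the protocol text itself.
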